**Title: Enhancing Spatial Navigation using Non-Invasive Brain Stimulation
NCT01958437**

PI: [name], ABPP/CN

Objectives: Remembering how to travel from one location to another is critical in everyday life, yet this vital ability declines with normal aging and can be further affected by conditions that disproportionately affect older adults, such as progressive dementia. Human and animal research has shown that two distinct memory systems interact during navigation. The first, referred to as allocentric navigation, is flexible and uses spatial knowledge of key features or landmarks to develop and use a mental map of the environment. This approach involves brain regions that are critical for new learning and memory but that decline with age. The second, referred to as egocentric navigation, is inflexible and relies on “habit” memories that link specific features with specific directions. This approach relies on brain regions that are critical for “automatic” responses and that are relatively unaffected by age.

The main problem is that allocentric navigation declines with age and is accompanied by increased dependence on egocentric navigation. This change increases the risk of becoming disoriented or “lost” when traveling in unfamiliar areas or even when traveling new routes in familiar areas. Therefore, **the main goal** of this project is to examine whether non-invasive brain stimulation, specifically transcranial direct current stimulation, can improve allocentric navigation in cognitively intact older adults and those who have been diagnosed with mild cognitive impairment (MCI) – a clinical precursor to Alzheimer’s type dementia.

Specific Aims/Hypotheses:

Specific Aim 1: Examine the effects of high definition tDCS (HD-tDCS) on both allocentric and egocentric memory test performance. We predict that participants will perform more accurately following active HD-tDCS when compared to sham HD-tDCS.

Specific Aim 2: Examine the neurophysiologic response to HD-tDCS using fMRI. We predict that active HD-tDCS will increase BOLD signal in a behaviorally meaningful way regardless of diagnostic group (i.e., healthy control vs. MCI). Critical questions about the restorative vs. compensatory effects of tDCS in those with MCI will be examined by contrasting BOLD signal change between the groups

Methodology

Participants: We will enroll up to 60 older adults (age 50+), who are right handed and MRI compatible, from the VA Ann Arbor Healthcare System, the University of Michigan Alzheimer’s Disease Center (MADC), and the surrounding community. Enrollment is open to participants regardless of race, gender, or social status.

Inclusion criteria: Patients will receive a diagnosis of MCI based on the Albert et al. (2011) criteria. Specifically, patients will **1)** report a subjective decline in memory (report can also be provided by an informant), **2)** demonstrate objective impairment in memory (based on Neuropsychological testing), and **3)** remain independent in activities of daily living. All patients will be stable on nootropic medications for at least 1-2 months prior to study initiation.

By definition, healthy controls (HC) will be free of objective memory test impairment (i.e., all scores within normal limits on the standardized testing protocol below).

Exclusion criteria: A history of **1)** contributory other neurological (e.g., epilepsy, moderate - severe traumatic brain injury) or medical conditions that are known to affect cognitive functioning; **2)** significant psychiatric conditions (e.g., moderate - severe depression, bipolar disorder, schizophrenia); **3)** sensory impairments that limit the ability to take part in the study; **4)** a significant history or current use of alcohol or drug abuse/dependence. Participants will also be screened to ensure MRI compatibility (assessed using the guidelines set forth by the American College of Radiology); some of the criteria for which are also reasons for excluding someone from tDCS (e.g., metallic or electronic implants). Eligible participants who cannot undergo MRI will be enrolled in the study and will complete only the stimulation and behavioral portions of the study. We have successfully used this same approach in our previous RCTs.

Recruitment: Participants will be recruited from both the VA Ann Arbor Healthcare system and the University of Michigan Alzheimer’s Disease Center. The primary recruitment source of MCI patients at the VA will be the Neuropsychology Clinic while HC will be recruited from the general VA community via postings/flyers in approved areas. The primary recruitment site for non-Veterans will be the University of Michigan Alzheimer’s

Disease Center (MADC). The MADDC recruits participants from several sources including its memory disorders clinic, community screening events, and external referrals. Participants interested in research are maintained in an IRB-approved database, which is available to the PI and his study team. This database includes individuals who are cognitively intact (HC) and those with MCI.

Screening & Cognitive Assessment: After providing informed, written consent, participants will undergo a brief neuropsychological protocol to ensure they continue meeting MCI criteria as outlined above (for patients) or that they are, in fact, cognitively intact (for the HC). This protocol includes standardized measures that are shown in the table below. Other measures may be added to the protocol to characterize the nature of the patient's cognitive functioning as necessary. Participants will be given breaks as necessary to ensure their comfort and are allowed to discontinue at any point for any reason.

Measure	Description	Screening Session
Montreal Cognitive Assessment (MOCA)	Gross screening measure for overall cognitive functioning (~5 minutes)	X
Wechsler Test of Adult Reading (WTAR)	Single word reading – used to establish premorbid intellectual estimates (~3 minutes)	X
Repeatable Battery for the Assessment of Neuropsychological Status (RBANS)	Brief Neuropsychological battery that includes Indices of attention, visuospatial, learning, memory, and processing speed. (~20 minutes)	X
Emory short version of Wisconsin Card Sorting Test (WCST)	Assesses the ability to identify possible solution strategies and abstract problem solving (~5-15 minutes)	X
Trail Making Test	Measures of psychomotor processing (Trails A) and set shifting (Trails B) (~3-10 minutes)	X
Temporal Sequencing Task	Novel Temporal Memory Task (~5 minutes)	X
Functional Activities Questionnaire (FAQ)	Evaluates patient's ability to perform everyday tasks (i.e., ADLs/IADLs) (~3 minutes)	X
Geriatric Depression Scale (GDS)	Evaluates current symptoms of depression (~3 minutes)	X
Multifactorial Memory Questionnaire (MMQ) & Memory Assessment Clinics – self report (MAC-S)	Self-report questionnaires that assess perceived memory complaints (~15minutes)	X
Object Location Touchscreen Test (OLTT)	Assesses the ability to learn and remember the location of objects (~10 minutes)	X
Screening protocol.		

Eligible participants move forward into the study, details of which are provided below.

Study Procedures:

Eligible participants will undergo 2 sessions within a 2-week period of time. Some degree of flexibility is necessary with these visits in order to accommodate both patient and MRI availability.

Once determined to be eligible, participants will be randomized to one of two groups within their respective diagnostic groups. The first group will receive active HD-tDCS during session 1 and then sham HD-tDCS during session 2. The second group will receive the opposite order.

Participants will first receive 20 minutes of HD-tDCS at 2mA or sham as appropriate to the assigned condition. Participant specific codes are entered into the Soterix Medical Inc Clinical Trial unit thereby ensuring participants and study staff are blinded to stimulation condition. Stimulation will be performed using a Soterix Medical Inc. tDCS unit (Clinical Trial system with attached 4x1 HD stimulation unit) within a quiet room. The unit automatically discontinues stimulation after the specified time has elapsed (here 20 minutes). The patient will

complete a brief questionnaire about the nature and severity of any side effects (see tDCS Safety below) as well as whether they believe they received active or sham stimulation.

The active tDCS protocol will provide an initial ramp-up period in which the electrical current is gradually increased, followed by 20 minutes of stimulation at 2mA, and finally a ramp down period during which the electrical current is gradually removed.

The sham tDCS group will receive a ramp-up period to 2mA followed immediately by ramp down period. This is repeated at the end of the session.

fMRI Scanning: After completing HD-tDCS, participants will be escorted to the MRI machine where they first undergo a resting-state fMRI scan and then complete the spatial navigation task. Structural imaging data were collected through a GE MR750 3T magnetic resonance system (GE, Milwaukee, WI) with a 32-channel phased array head coil. Sequence parameters for acquisition were: Field of view (FOV) = 256, Matrix = 256 × 256, 156 slices per volume, 1 mm³ voxel size, TR = 12 ms, TE = 5 ms, TI = 500 ms, flip angle = 15°. For resting state fMRI, participants were instructed to focus their gaze on the fixation cross on the screen and to not fall asleep. Resting state data was acquired through an echo planar imaging (EPI) multi-band sequence and parameters were: FOV = 240, Matrix = 74 × 74, 45 slices per volume, 3.4 × 3.4 × 3 mm voxel size, TR = 900 ms, TE = 30 ms, flip angle = 70°. For the functional task portion, participants were instructed to view the spacial navigation videos and remember key landmarks or series of turns depending whether it was allocentric or egocentric task. Functional task data was also acquired through an echo planar imaging (EPI) multi-band sequence with the following parameters: FOV = 220, Matrix = 88 × 88, 51 slices per volume, 2.5 × 2.5 × 2.5 mm voxel size, TR = 1200 ms, TE = 30 ms, flip angle = 70°.

Memory Testing: After scanning, participants perform a spatial navigation memory test that uses a touchscreen monitor to evaluate responding. Allocentric accuracy is measured as the distance (in CM) between the actual and selected location (lower values indicate greater accuracy) of a given landmark within a given map. Egocentric memory accuracy is evaluated by showing participants an image of a given environment after which they recall the sequence of turns through the environment. The dependent variable is the number of turns correctly recalled.

Statistical Design:

The primary analytic technique for the behavioral measures will be a repeated measures ANOVA (via the current version of SPSS). The effects of HD-tDCS for allocentric and egocentric performance will be examined separately. These analyses may include potential confounding factors as covariates.

fMRI data analysis MRI images were preprocessed and analyzed through SPM8 (SPM8; Wellcome Trust Centre for Neuroimaging). Slice timing correction was performed for functional volumes. Functional volumes were realigned to the first volume in the experiment to correct for head motion, co-registered with the high-resolution sagittal images. The structural images were spatially normalized to a standard MNI template using the voxel-based morphometry toolbox (VBM8 <http://dbm.neuro.uni-jena.de/vbm>) and DARTEL high-dimensional warping and resampled to a 3x3x3 mm voxel size. Estimated deformation fields from warping were applied to normalize images to MNI space, and smoothed using a 5-mm FWHM Gaussian kernel. Motion scrubbing (removal of volumes) was performed based on a framewise displacement threshold of 0.3. The time course data for each voxel was band-pass filtered (0.01 to 0.10 Hz band) to capture the low-frequency spontaneous BOLD oscillations in resting state signals.

Task analysis

For the spatial navigation task, preprocessed MRI data were analyzed with the general linear model framework in SPM8. Two block regressors were modeled: allocentric and egocentric. The onsets and durations of blocks were convolved with a canonical hemodynamic response function (HRF) to create the block regressors, in addition to covariates of six image realignment parameters to reduce movement induced artifacts. In the first-level analysis for each participant, the parameter estimates of block regressors were computed at each voxel. Appropriate linear contrasts were applied to the parameter estimates to produce contrast images and statistical parametric maps (SPM t map). To evaluate activations associated with task, session, and group effects, we've

constructed a mixed ANOVA model to test the influence of the aforementioned variables. Second-level maps were initially thresholded at whole-brain $p < .01$ to $.001$, uncorrected (extent threshold, $k = 10$). In addition to whole brain analysis, we also created a mask from activations seen in the whole brain analysis of task main effects (voxel-wise FWE $p < .05$) for use in group analyses of session effects. Specific regions of interests (ROIs) were also utilized, selected based on prior work (Hampstead et al., 2014) in regards to spatial navigation and derived from the Anatomical Automatic Labeling software (Tzourio-Mazoyer et al, 2002). These ROIs included hippocampus, superior parietal lobule, and caudate (all small volume corrected at voxel-wise FWE $p < .05$). Beta values of surviving brain activations were extracted and analyzed with ANOVA with significance threshold set at $p < .05$.

Resting state analysis

Resting state functional connectivity was first examined using a region of interest (ROI) "seed" at the stimulation site, right superior parietal lobule (rSPL), using a 10 mm radius spheres centered at MNI: (24, -60, 60). Pearson product-moment correlation coefficients were calculated between the average BOLD time course in the seed region and all other voxels in the brain. Each correlation resulted in a 3D correlation coefficient image (r-image). R-images were then transformed to z scores using a Fisher r to z transformation. Z score images from the individual functional connectivity analyses were entered into second-level random effects analyses (factorial ANOVA and t-tests) implemented in SPM8.

We have further applied a 'data-driven' approach based on Graph Theory to analyze the functional connectivity network before and after the intervention. We've used Power's 264 anatomical coordinates to segment the brain into 264 ROIs. We included additional medial temporal and subcortical ROIs. Each ROI was defined as a 5 mm sphere centered around these coordinates. A binary grey matter mask was created through the segmentation procedure in VBM8 and the threshold probability of 0.6 (as suggested by Zalesky et. al.) was used to overlay on the normalized resting state images. The average time course signal of the grey matter voxels in each ROI was measured. Pearson's correlation between the signal time course of all possible pairs of ROIs was conducted. Correlation weights that failed the false discovery rate (FDR) threshold at $p < 0.05$ were discarded. Graph parameters, including total functional connections, network strength, and network cost were calculated.

Within each group (HC and MCI), we will use the active > sham contrast to identify regions that differ as a result of HD-tDCS. Correlations between behavioral performance (e.g., accuracy in CM) and BOLD signal will also be calculated to determine whether the altered BOLD signal is behaviorally meaningful. Because we expect functional reorganization throughout the brain within both groups as a result of HD-tDCS, we intend to use connectivity analyses to examine changes in the connectivity between the parietal cortex and the remainder of the brain.

Exploratory between group analysis will use two primary contrasts. 1) HC sham > MCI sham – which will identify disease-related differences in activation between the groups; 2) HC active > MCI active – which will examine whether the tDCS-related changes are greater in one group than the other. Taken together, these contrasts will also clarify whether tDCS restores functioning in brain regions involved in "normal" (i.e., age appropriate) navigation or whether it allows MCI patients to recruit alternative brain regions in a compensatory manner.

Additional analyses will be performed as necessary in order to fully characterize the nature of tDCS-related changes.

tDCS Safety: tDCS has been used with literally thousands of patients world-wide. Brunonni et al., (2011) demonstrated that the rate of side effects is comparable between those receiving active and sham stimulation. We will follow current safety guidelines for dosing and will use a current strength of up to 2mA and duration of 20 minutes per session. Few, if any, side effects are reported with these parameters and those that are reported are mild in nature (e.g., tingling, itching, burning sensation, (Nitsche & Paulus, 2011). Importantly, we will collect data on tDCS-related adverse effects using the questionnaire provided by Brunoni and colleagues (2011). This questionnaire is provided below.

tDCS Adverse Effects Questionnaire – Session _____

Do you experience any of the following symptoms or side-effects?	Enter a value (1–4) in the space below (1, absent; 2, mild; 3, moderate; 4, severe)	If present: Is this related to tDCS? (1, none; 2, remote; 3, possible; 4, probable; 5, definite)	Notes
Headache			
Neck pain			
Scalp pain			
Tingling			
Itching			
Burning sensation			
Skin redness			
Sleepiness			
Trouble concentrating			
Acute mood change			
Others (specify)

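### One present-tense side-effect form per session, with no same-day baseline, no later rating and no session attribution, leaves the descriptive safety data incomplete and open to misfiling

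*Combined protocol and SAP*

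**What the plan says.** Under Study Procedures: "Eligible participants will undergo 2 sessions within a 2-week period of time", with some flexibility for scheduling and no minimum gap. The design is a two-period crossover within diagnostic group: "The first group will receive active HD-tDCS during session 1 and then sham HD-tDCS during session 2", and the other group has the reverse order.

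The same section describes the end of stimulation: "The unit automatically discontinues stimulation after the specified time has elapsed (here 20 minutes"). The next sentence has the patient "complete a brief questionnaire about the nature and severity of any side effects" and guess whether stimulation was active or sham. The fMRI Scanning section continues: "After completing HD-tDCS, participants will be escorted to the MRI machine". Memory Testing follows scanning. Neither section mentions a further symptom rating.

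The tDCS Safety section names this questionnaire as the means of collecting adverse-effect data and reproduces it. Its title, "tDCS Adverse Effects Questionnaire – Session", ends in a blank for the session number, so one form per session is implied. The lead question is "Do you experience any of the following symptoms or side-effects". There are ten named symptoms and an open row for others, with a four-level severity score, a five-level relatedness score headed "If present: Is this related to tDCS", and a notes column.

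**The concern.** A single present-tense rating shows only what the participant feels when the form is filled in. Three things fall outside it:

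- what was already there before the current was switched on, such as headache, sleepiness or poor concentration;
- what starts later, during scanning, during memory testing or after the participant has left;
- which session a lingering symptom belongs to.

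The third matters more here than in a parallel-group trial, because every participant changes condition between sessions. Anything carried over is recorded against the other condition. At stake is the completeness and attribution of the only safety data that the protocol describes.

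**Working it through.** The documents contain no side-effect rate, duration or safety calculation, so there is no figure to reproduce. The check is a count of ratings, followed by reasoning about where symptoms would be filed.

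**1. Ratings per participant**

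| Time point | Ratings described | Source |
|---|---|---|
| Before stimulation, same day | 0 | Study Procedures |
| After stimulation (timing by sentence order) | 1 per session | Study Procedures; tDCS Safety |
| After scanning or memory testing | 0 | fMRI Scanning; Memory Testing |
| Between sessions | 0 | Study Procedures |
| After session 2 | 0 | none described |

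Total: 1 × 2 sessions = 2 ratings per participant. The nearest thing to a baseline is the Geriatric Depression Scale in the screening table. It covers depression only and is not given on the day of stimulation.

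**2. What the form can recover**

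- *Pre-existing symptom.* The relatedness score can mark it as unrelated, and the notes can explain it. This partly replaces a baseline, but it relies on the participant's judgement and gives no earlier severity to subtract.
- *Effect starting after the session 1 form and gone by session 2.* Not captured, because the question is in the present tense and has no look-back period.
- *Effect starting after the session 2 form.* Not captured, because no later contact is described.
- *Effect from session 1 still present at session 2.* Captured on the session 2 form. The relatedness score asks about tDCS in general, so it can be scored as related and still be filed under the wrong condition.

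**3. Direction of the misfiling**

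Let n participants follow each order (equal numbers assumed; no allocation ratio is stated). Let pA and pS be the proportions with a symptom persisting to session 2 after active and after sham. Active-first participants add n × pA symptoms to the sham total. Sham-first participants add n × pS to the active total. The shift in (active minus sham) is therefore

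n × pS − n × pA = n × (pS − pA).

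This is zero if persistence is equal, and it narrows the contrast only if active symptoms persist more often. Neither proportion is in the documents, so neither the size nor the sign can be fixed from them.

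**4. Exposures concerned**

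Enrolment is up to 60. If all 60 complete and order is balanced (both assumptions), 60 / 2 = 30 receive active stimulation at session 2, with no later contact described. The other 30 receive it at session 1, and their next rating is at the sham session, up to about two weeks later. These are counts of exposures, not of expected side effects.

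**The case against.** The strongest case on the other side has five parts.

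**No conclusion depends on these data.** Neither Specific Aim concerns safety, and the Statistical Design and imaging analysis text contain no active–sham comparison of side effects. This stands. A reader might infer that the trial's side-effect comparison is biased toward finding active and sham alike. The documents do not support that: they plan no such comparison, and the remark in tDCS Safety about comparable rates describes a cited publication. As step 3 shows, misfiling also runs both ways.

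**Randomized order protects against background symptoms.** Pre-existing complaints are expected equally under both conditions, so the missing baseline mainly adds noise. This stands.

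**The form already has safeguards.** The relatedness, notes and open-row fields help with pre-existing symptoms. This stands in part: none of them identifies the session.

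**Timing and persistence are not stated.** The order of events is inferred from adjacent sentences. A reader might conclude that observation is confined to the minutes after switch-off, but no clock time is given. Nor do the documents say that effects are delayed or long-lasting; tDCS Safety expects few, mild ones. This limits any claim about size, not the observation that nothing would record such effects.

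**Silence is not proof.** Staff may hear spontaneous complaints, and the consent pages, which may contain reporting instructions, are not in the text available. A reader might also infer that someone reporting a severe effect at session 1 would be stimulated again without anyone seeing the report. The protocol is merely silent on who reads the form and when, and what should follow from such a report is a clinical matter outside this point.

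**Conclusion.** The point holds as a gap in the completeness and attribution of descriptive safety data. Each participant has two ratings, with none before stimulation, before departure, between sessions or after session 2, and the form cannot assign a persisting symptom to the session that caused it.

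The size of any resulting bias cannot be estimated, and its direction depends on persistence after active relative to sham, which is not given. The allocentric and egocentric comparisons are not directly affected.

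The conclusion rests on reading the form as completed once per session, after stimulation and before scanning. That is the natural reading but not an explicit one. It also assumes that no collection is arranged in material not available here. This is a cheap improvement, not a defect that threatens the trial's aims.

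**What to change.** Keep the present form and its current placement, and use it at contacts that already exist:

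1. Before stimulation at each session, as a same-day baseline.
2. At session 2, add to that pre-stimulation form an item asking about symptoms since the last session, and credit the answers to session 1's condition.
3. After memory testing at each session, before the participant leaves. This applies equally to participants who skip the MRI.
4. State the time of each rating in Study Procedures, and report symptoms as change from the same-day pre-stimulation rating.

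This gives 3 ratings per session, or 3 × 2 = 6 per participant in place of 2, plus the one look-back item. The cost is a few minutes per visit, with no added visit. The downside is that more mild, unrelated symptoms will be recorded; reporting change from baseline limits their influence. A short telephone check after session 2 is optional. Without it, effects arising after the final departure stay unobserved, and the report should say so.

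### Stimulation order is randomised, but no analysis commits to an order or period term; if order is left out, visit-to-visit change falls into the error term

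*Combined protocol and SAP*

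**What the plan says.** Study Procedures sets out two sessions within two weeks, in which "participants will be randomized to one of two groups within their respective diagnostic groups". It continues: "The first group will receive active HD-tDCS during session 1 and then sham HD-tDCS during session 2". The other group has the reverse order.

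The behavioural analysis takes three sentences in Statistical Design. The first is "The primary analytic technique for the behavioral measures will be a repeated measures ANOVA (via the current version of SPSS". The second says that allocentric and egocentric performance are analysed separately. The third is "These analyses may include potential confounding factors as covariates". Order, sequence and period are not mentioned.

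For imaging, Task analysis introduces its second-level model with "To evaluate activations associated with task, session, and group effects" and says that the team "constructed a mixed ANOVA model to test the influence of the aforementioned variables". A mask was also made "for use in group analyses of session effects". Resting state analysis refers to "second-level random effects analyses (factorial ANOVA and t-tests) implemented in SPM8" without naming the factors. Later in that section, an active-over-sham contrast is specified within each diagnosis, with no adjustment for visit.

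**The concern.** Participants do a navigation memory test at two visits close together, and the documents do not say whether different environments are used. Practice or another change between visits is therefore plausible. Randomising the order guards against bias from such a change, but the analysis gets the full benefit only if it separates the change from the stimulation effect. Otherwise the change adds to the apparent noise in the active–sham difference and, when the analysed orders are unequal, also moves the estimate.

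This affects the primary test of Aim 1 and the main contrast of Aim 2. The imaging subset may be unbalanced by chance even if randomisation was balanced, because people who cannot have MRI contribute only to the stimulation and behavioural parts (Exclusion criteria).

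**Working it through.** The plan contains no power or sample-size calculation, so there is no stated figure to reproduce.

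**What each model contains.** In Statistical Design the stimulation factor can be inferred, but order is only permitted. In Task analysis, *session* is undefined. If it means active versus sham, period is missing. If it means visit, as in Study Procedures, stimulation is missing from that model. Both would be present only if *group* meant the two order groups, but Specific Aims and the between-group contrasts use *group* for healthy control versus MCI.

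**Inputs.** From the documents: two orders, randomised within two diagnoses, and up to 60 participants. Assumed, because not stated: N = 60 in total and N = 30 for one diagnosis; a two-sided 5% test; an effect δ = 0.4s; a session 2 minus session 1 shift π between 0 and 1.0s; no carryover. Here s is the within-order SD of the active–sham difference.

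**Model.** d = δ + kπ + e, with SD(e) = s, k = +1 if active came second and −1 if it came first. The difference d is regressed on an intercept (plus diagnosis at N = 60), without or with order coded −1/+1, and the intercept is tested. Each cell has 100,000 simulated runs.

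**1. Equal orders, order omitted.** The estimate is centred on δ. The expected error variance is s² + π²·N/(N − g), with g diagnostic groups. At N = 60 and g = 2, N/(N − g) = 60/58 = 1.034. The variance is multiplied by
- 1 + 0.0625 × 1.034 = 1.065 at π = 0.25s
- 1 + 0.25 × 1.034 = 1.259 at 0.5s
- 1 + 1.034 = 2.034 at 1.0s

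| π | Power without/with order, N = 60 (30:30) | Power without/with order, N = 30 (15:15) |
|---|---|---|
| 0 | 86/86% | 56/56% |
| 0.25s | 85/86% | 54/56% |
| 0.5s | 80/86% | 47/56% |
| 1.0s | 60/86% | 25/56% |

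**2. Unequal orders, order omitted.** With n₁ people having active second and n₂ having it first, the estimate shifts by π(n₁ − n₂)/N: 12/60 = 0.20π at 36:24 and 10/30 = 0.33π at 20:10.

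| Split | Type I error at π = 0.25s | 0.5s | 1.0s |
|---|---|---|---|
| 30:30 | 4.3% | 2.8% | 0.6% |
| 34:26 | 5.0% | 4.9% | 3.9% |
| 18:12 | 5.2% | 5.3% | 4.7% |
| 36:24 | 5.9% | 7.8% | 11.0% |
| 20:10 | 6.4% | 10.1% | 17.2% |

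With order in the model it is 4.9–5.1% throughout.

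**3. How likely such splits are.** Under unblocked 1:1 allocation (the scheme is not stated), a split of 36:24 or worse has probability 0.155 at N = 60, and 20:10 or worse has probability 0.099 at N = 30. Averaged over all unblocked splits, type I error without order is about 5%.

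**4. How order is entered.** If order is an uncentred 0/1 covariate and the stimulation test is read at code 0, the test concerns one order only and targets δ plus or minus π. At 30:30 its type I error is 27%, 77% and over 99% at π = 0.25s, 0.5s and 1.0s.

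**5. Cost when π = 0.** With order, the variance of the estimate is s²(1/n₁ + 1/n₂)/4. At 36:24 this is 0.01736s² against s²/60 = 0.01667s²; at 20:10 it is 0.0375s² against 0.0333s². Power from the noncentral t distribution changes as follows:
- N = 60: 86.1% to 85.5% (34:26) or 84.7% (36:24)
- N = 30: 56.3% to 54.5% (18:12) or 51.4% (20:10)

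The adjusted estimate has the smaller mean squared error once π exceeds √[(1/n₁ + 1/n₂)/4 − 1/N] ÷ (|n₁ − n₂|/N), in units of s. This is √0.000694/0.20 = 0.13s at 36:24 and √0.004167/0.333 = 0.19s at 20:10.

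**The case against.** The plan does not exclude order, since the covariate clause allows it. Aim 1 and Statistical Design also make clear that active versus sham is tested, and the active-over-sham contrast does the same for imaging. This is fair: the gap is a missing commitment, and nothing in the plan rules order out.

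The harm depends on a shift that the documents do not give. With equal orders there is no bias and the test errs on the conservative side. Averaged over unblocked splits at N = 30, power without and with order is 56.3% and 54.8% at π = 0, 53.6% and 54.8% at 0.25s, and 47.6% and 54.8% at 0.5s. With a small shift the change is close to break-even. The excess type I error also needs an uneven split. All this stands and limits the weight of the point, but it does not justify leaving the model open when order is known and adjustment costs little.

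Nobody has proposed the uncentred 0/1 coding. That is true, and those figures are only a caution. They are relevant because covariates are the only route the plan offers for order.

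Finally, order adjustment does not deal with carryover, and no minimum gap between sessions is stated. If active carried 0.2s into a following sham session, one order would show 0.4s − 0.2s = 0.2s and the other 0.4s. The average would be 0.3s, with power of about 63% at N = 60 with or without order. This is a limit of the design that both analyses share.

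**Conclusion.** The concern holds and should be fixed. The behavioural ANOVA does not commit to order, and no imaging model is stated to hold both stimulation and period. The consequence is mainly lost power: negligible at a shift of 0.25s, about 6 points at 0.5s and 26 points at 1.0s for N = 60 with equal orders. With clearly uneven orders the estimate is also displaced, and type I error reaches 7.8% (36:24) or 10.1% (20:10) at 0.5s. That excess is conditional on the realised split. The textual finding is firm. The sizes rest on the assumed effect, shift, sample sizes and absence of carryover.

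**What to change.** - **Behavioural ANOVA.** State stimulation (active/sham) as the within-person factor, with randomised order and diagnosis as between-person factors. Include the stimulation-by-order term, which is the period effect. Take the stimulation effect as the equally weighted average over the two orders, and do not enter order as an uncentred 0/1 covariate.
- **Task and resting-state second-level models.** Define the tested factor as active versus sham and add session number (1 or 2) as a nuisance term.
- **Separate wording point, with no bearing on the weight above.** The graph-theory paragraph describes a pre–post comparison, but the only resting scan described under fMRI Scanning follows stimulation. Describe that comparison as active versus sham within person.

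The cost is one or two degrees of freedom. If there is no visit shift, power is unchanged with equal orders and falls by at most about 5 points in the splits examined (20:10). The behavioural change is wording only. Most imaging models are described in the past tense, so any already run would need re-fitting.
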